### **10.13. Serious Adverse Event Reporting Requirements**

If an SAE occurs, Xeris Pharmaceuticals is to be notified within 24 hours of awareness of the event by the investigator. In particular, if the SAE is fatal or life-threatening, notification to Xeris Pharmaceuticals must be made immediately, irrespective of the extent of available AE information. This time frame also applies to follow-up on previously forwarded SAE reports.

In the rare event that the investigator does not become aware of the occurrence of an SAE immediately (e.g., a study subject initially seeks treatment elsewhere), the investigator is to report the event within 24 hours after learning of the event and document the time of first awareness of the AE.

A death occurring during the study, during the protocol follow-up period, or within 30 days after stopping treatment with test drug must be reported to Xeris Pharmaceuticals or its designee(s) immediately, whether or not it is considered treatment-related. Initial SAE reports must be followed by detailed descriptions. These should include copies of hospital case records and other documents when requested. Telephone and e-mail reports must be confirmed promptly either by facsimile or by overnight courier or mail.

### **10.14. Non-Serious Adverse Event Reporting Requirements**

All AEs will be reported on the AE page(s) of the CRF. AEs should be reported using concise medical terminology on the CRFs as well as on the form for collection of the SAE information.

### **10.15. AE Reporting Requirements to Regulatory Authorities**

AE reporting by the Sponsor, including suspected serious unexpected adverse reactions, will be carried out in accordance with applicable regulations.

The investigator must notify the IRB of the occurrence of any SAE, in writing, as soon as is practicable and in accordance with local regulations. A copy of this notification must be provided to Xeris Pharmaceuticals or its designee.

In the event of an SAE that meets the criteria for expedited reporting, an SAE report will be prepared for submission to the FDA and any other applicable authorities by the Sponsor or its designee.

### **10.16. Pregnancy**

The active pharmaceutical product in Xeris Pharmaceuticals' glucagon formulation is glucagon, which is in Pregnancy Category B. Female subjects able to become pregnant will be tested (rapid, urine) for pregnancy at the Screening visit. Any subject found to be pregnant at the Screening visit (Visit 1) will not be randomized into the study. Pregnancy testing will be repeated prior to each induced hypoglycemia procedure (i.e., Visits 3, 7, 9 and 11). Any subject who is found to be pregnant at one of the treatment visits will be withdrawn from the study immediately and no further study treatments will be given, nor will induced hypoglycemia procedures be performed. Pregnancy at the follow-up visit will be noted, but the visit will be

completed. Any pregnancy in a subject who received at least one dose of study drug will be followed until resolution (i.e., birth or voluntary or spontaneous termination of the pregnancy). Any pregnancy outcome that meets the criteria for an SAE will be reported as an SAE.

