## 7. STUDY DESIGN

### 7.1. Study Overview

This is a prospective, randomized, double-blind, parallel trial with the primary analysis after 4 weeks treatment with CSGI or placebo. As both the low and high dose group use the same formulation, the dose will be determined by infusion. To preserve the blind, the placebo therefore is administered by matching infusion methods to CSGI (high and low infusion rates, split to create the appearance of a 4-group trial on the schematic).

Study Schematic:

After a 1-week run-in on CGM, subjects will have key hormones of their hypoglycemia counter regulatory response quantified using a stepwise hypoglycemia induction. They will then receive investigational product for 4 weeks before discontinuation and reassessment of the same hypoglycemia counter regulatory response.

Treatment stops at 4 weeks, but subjects will continue blinded for 6 additional months to investigate duration of response with assessments at 3 and 6 months. The primary endpoint will be tested at 4 weeks post randomization, but the double blind will remain intact until the end of the study.

Baseline Qualification:

Subjects will continue their insulin regimen as usual throughout the study, adjusted by the investigator to achieve ADA recommended targets.

After enrollment, the subjects will require approximately one week of CGM data prior to their baseline hypoglycemia induction procedure. Subjects will enter a run-in phase of 1 week wearing a blinded CGM device.

Subjects will arrive in the Clinical Research Unit (CRU) the morning of the planned hypoglycemia induction procedure. The CGM data will be retrieved. The following CGM criteria must be met: a minimum of 6 days must be recorded using the CGM before the subject will be fitted with a new CGM device. If the CGM criteria are not met, the subject is inserted with another CGM for renewed baseline period. Should the second baseline period not yield eligible CGM data, the subject will stop further participation in the screening procedures.

The subject will fast after midnight. The subject's arms are cannulated venously, one side for both insulin and glucose infusion and the other side for venous sampling. The subject will stop their own insulin treatment and receive IV insulin and IV glucose to maintain their plasma glucose between 80 to 120 mg/dL, as measured by either BGM or YSI. They will remain fasting until the end of the hypoglycemia procedure the following day.

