19. At the end of the treatment visit, the subject will discontinue use of the iPRO2mylog.
20. For the rest of the study, the subject will continue their standard of care for diabetes management. Study drug and devices are no longer used.

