**9.5.10. Visit 9 (Week 13±1 Week) 3-Month Follow Up**

The subject will arrive to the clinic at about 6-9 am the day of the planned hypoglycemia induction procedure. The subjects will undergo this inpatient CRU visit.

1. AEs since the last visit will be recorded.
2. Concomitant medication review.
3. Assessment of vital signs, including measurement of BP, after a 5-minute seated rest
4. Urine pregnancy test for women of childbearing potential.
5. The subject will be reminded to refrain from using his or her own insulin until the hypoglycemia induction procedure is complete.
6. The subject will complete the Gold Scale

7. Subject data including CGM, insulin utilization, electronic diary data will be uploaded to the MedTronic iPRO2 platform.
8. The Insulin Diary will be collected from the previous visit.
9. IV lines are inserted in both upper extremities for IV insulin and glucose infusion, and for venous sampling.
10. Plasma glucose is measured using a laboratory quality instrument, e.g. the YSI 2300 or 2900 that will be used for the clamping procedure.
11. Plasma Glucose will be maintained in the 80-120 mg/dL range as described in section 9.4.
12. The subject will undergo the hypoglycemia induction procedure and normalization to euglycemia, per Section 9.4
13. The subject will have the following sample drawn:
  - Immunogenicity Sample

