#### **9.5.12. Visit 11 (Week 26±1 Week)**

##### **6-Month Follow Up and Completion of Study**

The visit procedures are identical to those on Visit 9 as described in section 9.5.9 with the additions that the following is performed:

1. A physical examination, excluding breast, pelvic and genitourinary exams.
2. The subject will have the following samples drawn:
  - CBC/CMP
3. Final discharge of the subject from the study.

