### **15. DEFINITION OF END OF TRIAL**

Last Subject Last Visit (LSLV) for each site is defined as the date the last subject at that site completes the 6-month follow-up visit (Visit 11).

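### Section 10.16 bars the hypoglycemia induction in pregnancy only at undefined treatment visits, so its most natural reading lets the induction go ahead at Visits 9 and 11

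*Protocol*

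**What the plan says.** Protocol Section 10.16 fixes the tests after screening by visit number: "Pregnancy testing will be repeated prior to each induced hypoglycemia procedure (i.e., Visits 3, 7, 9 and 11"). It then states two actions, neither tied to a visit number.

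- First: "Any subject who is found to be pregnant at one of the treatment visits will be withdrawn from the study immediately". Such a subject also gets no more study treatment and no induction.
- Second: "Pregnancy at the follow-up visit will be noted, but the visit will be" completed.

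The rest of the protocol describes Visits 9 and 11 as follows.

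- Section 7.1: "Treatment stops at 4 weeks, but subjects will continue blinded for 6 additional months". At the end of Visit 7, Section 9.5.7 says: "Study drug and devices are no longer used".
- Visit 9 is titled the 3-month follow-up (Section 9.5.10). Its last steps include: "The subject will undergo the hypoglycemia induction procedure and normalization to euglycemia, per Section 9.4".
- Visit 11 is titled the 6-month follow-up (Section 9.5.12): "The visit procedures are identical to those on Visit 9 as described in section 9.5.9". In the body Visit 9 is in fact Section 9.5.10, but the visit is named, so the meaning is clear.
- Section 15 defines the end of trial by the date on which the last subject "completes the 6-month follow-up visit (Visit 11").
- Table 6 marks both the pregnancy test and the induction at Visits 9 and 11.

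**The concern.** The pregnancy test precedes the induction at all four visits, yet the only stated bar on the induction depends on whether the visit is a treatment visit. At two of the four visits the better-fitting label is follow-up, and the rule for follow-up is to finish the visit. The protocol itself treats induced hypoglycemia as something to withhold from a pregnant subject, so a rule that can be read to allow it at Visits 9 and 11 is a gap in subject safety. It also lets sites act in opposite ways on the same positive test. No efficacy inference is at stake.

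**Working it through.** No plan figure needs reproducing. The check sets the passages side by side.

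**Step 1. Which visits carry both a test and an induction?** Visits 3, 7, 9 and 11 (Section 10.16, Table 6). Screening has a test but no induction. Visits 4, 5, 6, 8 and 10 have neither.

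**Step 2. What does completing Visit 9 or 11 involve?** In Section 9.5.10 the pregnancy test is item 4 and the induction is item 12, with no stop instruction between them. Visit 11 repeats these procedures and adds a few more. Completing either visit as listed therefore includes the induction.

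**Step 3. Try each meaning of treatment visit.**

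| Meaning of treatment visit | Support in the protocol | Result of a positive test at Visit 9 or 11 |
|---|---|---|
| Visits 3 and 7, or all of Visits 3 to 7 | Titles of Visits 9 and 11; Section 15; treatment ends at Week 4 (Sections 7.1, 9.5.7); weakly, Table 8 note b, which counts two treatment visits | Noted, visit completed, induction not barred |
| All four induction visits | The visit list in the preceding sentence of 10.16; bedside glucose at treatment visits (Section 10.2); Appendix 1, which applies treatment wording to Visits 3, 7, 9 and 11; Appendix 2 | Withdrawn and no induction under the first rule; visit completed under the second |

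The first row is the more natural, because it agrees with the visit titles and with the end of dosing. Whether it means Visits 3 and 7 only or every visit from 3 to 7 makes no difference at Visits 9 and 11. Table 8 note b is weak support because it concerns the drug screen, which Table 6 places at Visits 1 and 7 only.

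**Step 4. Does another passage settle it?** None does. Section 8.2, item 21, requires contraception during the study but does not address a later positive test. Table 8 note a says testing is repeated at the last treatment visit, which does not match the four visits in Section 10.16. Section 9.6 sends withdrawn subjects to the assessments in Section 9.5.11. That number is Visit 11, with its induction, in the table of contents, but Visit 10 in the body, so the withdrawal route does not clearly exclude an induction either.

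**Step 5. What would the subject be exposed to?**

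- Synopsis and Section 7.1: 30 minutes at 50 ± 5 mg/dL, then hormone samples, then insulin is stopped. Minimum 30 minutes.
- Section 9.4.4: 30 continuous minutes, then two samples 10 minutes apart, for example at 30 and 40 minutes. About 30 + 10 = 40 minutes.
- The range is 45-55 mg/dL in Table 5. Section 9.4.4 caps glucose at 54 mg/dL, and SAP Section 7.2.9 uses 45-54.

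The statement that holds across sections is at least 30 minutes near 50 mg/dL, and about 40 under Section 9.4.4.

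**The case against.** The strongest reply is purpose. Testing is ordered before each induction, and study drug has ended by Visits 9 and 11, so a test there has little use unless a positive result stops the procedure. General safeguards point the same way: investigators may withdraw a subject for safety (Section 9.6), subject well-being is to be protected (Section 10), and an investigator is on site during inductions (Section 10.17). This stands as evidence of intent and makes an actual induction in a pregnant subject unlikely. It does not cure the text. None of these passages is a pregnancy stop rule, and the sentence that does address follow-up says the visit is completed.

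A second reply is that the follow-up sentence can be given harmless work. Visits 8 and 10 prepare for the follow-up inductions and include adverse event review but no induction, and a withdrawn subject is asked back for a final visit. Noting a pregnancy and finishing the visit would be reasonable there. A reader might infer that on the broad reading the sentence has nothing to govern, and this reply shows that inference goes too far. But nothing limits the sentence to those visits, and Section 15 gives the name of follow-up visit to Visit 11.

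A reader might also infer that most on-study pregnancies would surface at Visits 9 and 11, because most of the time between scheduled tests leads up to them. The documents do not support that. It is a share of calendar time, and it assumes that no pregnancy is recognised or disclosed between tests.

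**Conclusion.** The point holds. On the most natural reading of Section 10.16, a subject known to be pregnant at Visit 9 or 11 would complete the visit, induction included. On the broader reading, the follow-up sentence conflicts with the bar at those visits. Two of the four inductions are affected, each with at least 30 minutes near 50 mg/dL.

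This rests on the ordinary sense of the visit titles and of completing a visit, since the protocol defines neither treatment visit nor follow-up visit by number. It does not show that the sponsor means pregnant subjects to be induced; the probable intent is the opposite. The event should be rare given the contraception requirement. No frequency can be stated, because the documents give no sex mix or pregnancy rate. The Week 4 primary endpoint, its alpha and its power are not affected. The paragraph should be corrected because it is a safety rule whose literal reading gives the wrong action.

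**What to change.** Replace the two action sentences in Section 10.16 with text along these lines:

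> No hypoglycemia induction will be performed in a subject known to be pregnant, at any visit (Visits 3, 7, 9 and 11). A subject found to be pregnant by any means from Visit 3 through Visit 7, including Visits 4-6, is withdrawn and receives no (further) study treatment. If pregnancy is found after Visit 7 (including at Visits 8-11), it is noted and only the non-induction assessments of the visit are completed.

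Three features matter. Visits 4-6 are named because subjects are on the pump then and start a new Omnipod at those visits. The trigger is pregnancy found by any means, so a pregnancy learned outside a scheduled test is covered. The bar applies while the subject is known to be pregnant, and adds no exclusion from later visits once a pregnancy has ended. Following a pregnancy to its resolution stays as written. Table 8 note a and the Section 9.6 cross-reference should be brought into line at the same time.

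The cost is one protocol paragraph and, rarely, a missing 3- or 6-month hormone value.

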### **10.17. Subject Monitoring**

Subjects will be monitored for AEs throughout the study by the study staff. The principal investigator or designated sub-investigator will be on site for drug administration initiation and during hypoglycemia induction procedures. If necessary, a physician, either at the study site or in a nearby hospital, will administer treatment for any AEs.

Safety parameters, including laboratory results and ECGs, will be assessed by the principal investigator or his/her delegate using the site's criteria for clinical laboratory and ECG acceptance ranges as suggested guidelines in making the medical assessment.

Scheduled safety measurements will be repeated according to appropriate SOPs or upon request from a physician. Any abnormal repeated measurement will be evaluated by a physician and repeated if judged necessary. Further action may be taken on the physician's request.

Subjects will be advised to notify their health care professionals (e.g., physician, dentist, and/or pharmacist) that they are participating in a clinical research study of a drug called synthetic Glucagon Injection before taking any medicines or undergoing any medical procedure.

## 11. DATA ANALYSIS AND STATISTICAL METHODS

Descriptive and inferential statistical methods will be used to summarize the data from this study. Unless stated otherwise, the term “descriptive statistics” refers to number of subjects (n), mean, median, standard deviation (SD), minimum, and maximum for continuous data and frequencies and percentages for categorical data. For some data that may be presented as continuous variables, there may be scientific reasons to present that data in constructed categories as well (e.g., BMI). Reasons for the categories will be described in the Clinical Study Report (CSR). Graphical displays may be presented for selected results.

A stand-alone Statistical Analysis Plan (SAP) will be written to describe in detail all statistical analyses planned for the study. It will be accompanied by mock Tables, Figures, and Listings. The SAP will be finalized and approved by signature and dates prior to database lock. The SAP will take precedence over the protocol for details about the statistical analyses for the study. In addition to the SAP, other graphical representations of the results may be produced after review of the data (post hoc).

Verbatim terms recorded for medical history conditions and adverse events will be mapped to a System Organ Class (SOC) and preferred term using the Medical Dictionary for Regulatory Activities (MedDRA) and all prior and concomitant medications will be coded using the World Health Organization (WHO) Drug Dictionary.

### 11.1. Efficacy

The primary aim of the study is to evaluate change from baseline of plasma epinephrine concentration during induced hypoglycemia with PG <50 mg/dl between placebo and CSGI after 4 weeks of blinded treatment. The null hypothesis to be tested is there is no difference in the change from baseline to 4 weeks between the two groups for plasma epinephrine concentration during induced hypoglycemia with PG <50 mg/dl. Two-group t-test will be implemented for each hypothesis test.

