### **6.1.2.3. Glucagon Infusion Rate Selection**

A previous study (Edelman, ADA annual scientific sessions, 2006) evaluating continuous glucagon administration for the prevention of hypoglycemia tested doses at 2, 4 and 8 ng/(kg\*min) and found apparently no effect at 2 ng/(kg\*min), weak indications of effect at 4 ng/(kg\*min) and, given a modest sample size, reasonably clear effect at 8 ng/(kg\*min) with some but limited room for further effect.

These findings would suggest doses in the vicinity of 4 and 16 ng/(kg\*min) corresponding to 19.2 and 76.8 µg/hr for an 80-kg person would be well chosen in this proof-of-concept study. As further development would most likely lead to a device with a fixed infusion rate, the glucagon doses chosen for the study are 20 and 80 µg/hr, or given the formulation concentration of 5 mg/ml, infusion rates of 4 and 16 µl/hr. For the pump setting that measures in insulin U100 units that corresponds to 0.4 and 1.6 U/hr.

This highest dose to be tested in the study will allow a greater than 10x safety margin based on findings from a 28-day toxicology study in rats conducted with Xeris glucagon (see current Investigator's Brochure).

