### **8.4. Allocation to Treatment**

Subjects will be assigned a unique Screening number upon entry in the eCRF, which will consist of a unique 2-digit site code (starting with 01) and a 2-digit subject number (starting with 01 at each site) indicating the sequence at which the subject was screened for eligibility. Subjects will keep this number throughout the study.

The randomization scheme is 1:1:1 for high dose, low dose and placebo. Each group will have 16 subjects, but the placebo group will be matched to high and low infusion rates (8 in each group). The randomization is stratified by site.

When the subject is qualified and the hypoglycemia induction procedure begins day 1, the subject will be randomized by the study coordinator by either a central randomization or by logging into the IWRS and requesting a treatment allocation. The site personnel will receive the blinded treatment allocation number for the study drug product.

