### **11.1.3. Sample Size Calculation:**

The primary hypothesis is to evaluate change from baseline to 4 weeks of plasma epinephrine concentration after 30 minutes of induced hypoglycemia with plasma glucose <50mg/dL between treatment groups. Sample size is based on a closed hierarchical hypothesis test as described above in section 13.1.1.

Using this method, an alpha of 5% will be preserved for each hypothesis test where the next ordered test will only be conducted if statistical significance is achieved for that hypothesis. Final calculations are based on 80% power and an alpha of 5%, to demonstrate a plasma epinephrine increase compared to placebo of 1.5 nmol/l given and SD of 1.34 nmol/l at an induced PG of 50 mg/dl. Sixteen subjects per treatment group (CSGI high dose, CSGI low dose, and placebo) are required based on the minimum sample size estimate for a comparison.

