### **7.10.2 Primary Efficacy Analysis**

The analysis of the primary endpoint will be performed using a two-group t-test for each treatment comparison of interest. The primary endpoint will also be analyzed, stratifying by duration of diabetes (<15 yrs, ≥15 yrs) as a secondary analysis.

A closed testing hierarchical procedure will be used to control for multiplicity. See section [7.10.5](#).

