### **7.10.4 Secondary Endpoints**

- Intravenous glucose infusion rate (GIR) [time frame: 0-30 mins induced hypoglycemia] (cumulative glucose infusion rate required to maintain insulin-induced hypoglycemia)
- Intravenous insulin infusion rate [time frame: 0-30 mins induced hypoglycemia] (cumulative insulin infusion rate required to maintain insulin-induced hypoglycemia)
- Change from Induction 1 (baseline visit) to Induction 2 (visit 7, Week 4) in other counter regulatory hormones (norepinephrine, glucagon, cortisol and growth hormone plasma concentrations) after 30 mins of induced hypoglycemia
- Change from Induction 1 (baseline visit) to Induction 2 (visit 7, Week 4) in Neuroglycopenic Symptom Scores (if hypoglycemia present) as documented using the hypoglycemia symptom questionnaire
- Change from Induction 1 (baseline visit) to Induction 2 (visit 7, Week 4) in Autonomic Symptom Scores (if hypoglycemia present) as documented using the hypoglycemia symptom questionnaire
- Change from baseline to Week 4 in CGM-derived hypoglycemia parameters of:
  - Proportional time spent with interstitial glucose <70, 60, and 50 mg/dL

- Rate of hypoglycemic event episodes at thresholds of plasma glucose <70, 60, and 50 mg/dL
- Area over the curve (AOC) of the reduction from baseline in the interstitial glucose from T0 to Tx, where x corresponds to time when interstitial glucose < 70, <60 and <50 mg/dL is achieved.
- Change from baseline to Week 4 in CGM-derived parameters of:
  - Average interstitial glucose and standard deviation
  - Proportional time within  $70 \leq \text{interstitial glucose} < 180$  mg/dL
  - Proportional time with  $\text{interstitial} \geq 180$  mg/dL
- Change from Induction 1 (baseline visit) to Induction 2 (visit 7, Week 4) in the Gold scale as a measure of hypoglycemia awareness

Pharmacodynamic endpoints (e.g., CGM derived parameters, counter regulatory hormones, GIR, insulin infusion rate) will be analyzed using a 1-factor (treatment) analysis of variance (ANOVA) model with treatment as the main effect.

The change from baseline for Gold scale, Neuroglycopenic Symptom Score, and Autonomic Symptom Score endpoints will be analyzed using non-parametric analysis of variance (Wilcoxon rank-sum test).

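### The gating combined-versus-placebo t-test merges the two randomised dose arms, so a true dose difference adds to its error; a contrast built from the three arms recovers a modest amount of power (minor)

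*Protocol*

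**What the plan says.** Protocol 8.4: "The randomization scheme is 1:1:1 for high dose, low dose and placebo", with 16 subjects per group.

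Protocol 11.1: "Two-group t-test will be implemented for each hypothesis test". SAP 7.10.2, which takes precedence over the protocol on analysis: "The analysis of the primary endpoint will be performed using a two-group t-test for each treatment comparison of interest".

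Protocol 11.1.1 and SAP 7.10.5 put CSGI combined versus placebo first, and testing stops if it is not significant at 5%. Neither document says whether the t-test is pooled or Welch. Neither gives a dose term or contrast for the primary endpoint.

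For pharmacodynamic secondary endpoints, including counter-regulatory hormones, SAP 7.10.4 says they "will be analyzed using a 1-factor (treatment) analysis of variance (ANOVA) model with treatment as the main effect".

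The sample size (Protocol 11.1.3, SAP 5) rests on one effect, a "plasma epinephrine increase compared to placebo of 1.5 nmol/l", and one "SD of 1.34 nmol/l at an induced PG of 50 mg/dl". The dose rationale (Protocol 6.1.2.3) cites an earlier infusion study with apparently no effect at 2 ng/(kg*min), "weak indications of effect at 4 ng"/(kg*min), and a reasonably clear effect at 8. The study doses of 20 and 80 µg/hr correspond to roughly 4 and 16 ng/(kg*min) at 80 kg.

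**The concern.** Dose is a randomised factor, so variation between the high and low arms is known structure rather than noise. A two-group t-test on the merged 32 subjects cannot separate the two. Any true gap between the doses enlarges the CSGI group's variance, and with it the standard error of the gating comparison.

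The dose rationale suggests that the doses may well differ, which is when the merged test is least efficient. Because this test decides whether any pairwise dose comparison is made at all, power lost here is lost to the whole hierarchy.

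**Working it through.** **Inputs.** Alpha 5% two-sided (SAP 7.10.1 hypotheses), SD 1.34 nmol/l and effect 1.5 nmol/l (Protocol 11.1.3), 16 per arm (Protocol 8.4). Assumptions: normal data, SD 1.34 within each arm, high-dose effect 1.5, and low-dose effect anywhere from 0 to 1.5. The documents give no dose-specific effects.

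**The plan's own figure.** For a two-sample t-test with effect 1.5 and SD 1.34, power is 78.2% at 13 per arm and about 81% at 14. So 14 × 3 = 42, which matches the N=42 in the synopsis. At 16 per arm, pairwise power is 86.5%.

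**How merging enters the error.** With gap g between the dose means, the expected variance of the merged group is 1.34² + (g/2)² × 32/31.
- g = 1.0: 1.796 + 0.258 = 2.054, SD 1.43.
- g = 1.5: 1.796 + 0.581 = 2.376, SD 1.54.

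**Standard error of the gate at g = 1.5.**
- By arm: √(1.796/64 + 1.796/64 + 1.796/16) = √0.168 = 0.410.
- Merged, Welch: √(2.376/32 + 1.796/16) = √0.186 = 0.432.
- Merged, pooled: error variance (31 × 2.376 + 15 × 1.796)/46 = 2.187, so √(2.187 × (1/32 + 1/16)) = 0.453.

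The pooled test suffers most because it also applies the inflated variance to the placebo mean.

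**Gate power (%), high-dose effect 1.5.** The estimated difference is the same in all four tests (equal arm sizes). Only the error term and its degrees of freedom change.

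| Low-dose effect | Welch t-test | Satterthwaite contrast | Pooled t-test | Common-variance contrast (45 df) |
|---|---|---|---|---|
| 1.5 | 94.2 | 94.2 | 94.7 | 94.7 |
| 0.75 | 75.0 | 75.7 | 74.8 | 76.5 |
| 0.5 | 63.8 | 65.2 | 62.9 | 66.5 |
| 0 | 38.6 | 42.3 | 35.6 | 43.2 |

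The first three columns are simulated, and repeat runs differ by up to about 0.3 point. The last column follows from the noncentral t with noncentrality ((high + low)/2)/(1.34 × √(1.5/16)).

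Like for like, the gain from Welch to Satterthwaite is 0, 0.7, 1.4 and 3.7 points. From pooled t-test to common-variance contrast it is 0, 1.7, 3.6 and 7.6 points.

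**Type I error.** With no effect and equal SDs, all four tests hold 5%. If only the high-dose SD is 1.5 or 2 times larger (an assumption), a common-variance three-arm model gives high versus placebo an error rate of about 6.7% or 8.2%, while the separate t-test stays near 5%. Low versus placebo falls to about 2.1% or 0.8%. The Satterthwaite gate contrast stays at about 5%.

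**The case against.** The planned test is valid, pre-specified, the same in both documents, and matches the sample-size method. Under the plan's single effect of 1.5 nmol/l in both doses, nothing is lost. The evidence that the doses differ comes from an earlier study of hypoglycaemia prevention, not of epinephrine response. All of this stands, and it makes the point one of efficiency, not error control.

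Three stronger readings are tempting, and the documents support none of them.

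- A reader might infer that a three-arm model gains 8 points at no cost. That figure needs a pooled t-test, which the documents do not specify, and a wholly inert low dose. The dose rationale reports weak indications of effect near that dose, not none. A common-variance model also has a cost: it borrows the third arm's variance in the pairwise steps and can distort their type I error, as shown above.
- A reader might infer that epinephrine alone among the hormones is denied an ANOVA. SAP 7.2.9 lists epinephrine among the counter-regulatory hormones, and planned Tables 14.2.2.4.1 and 14.2.2.4.2 apply ANOVA to those hormones. A supportive epinephrine ANOVA is therefore arguably planned already.
- A reader might infer that the contrast rescues the gate. With an inert low dose it still has only about 42% power, against 86.5% for high dose versus placebo tested alone. That shortfall comes from placing the combined test first, which this change does not touch.

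**Conclusion.** The point holds as a minor one. The gating test counts a true dose difference as error and so gives up some power when the doses differ. The size is about 0 to 4 points if the t-test is Welch and the contrast uses arm-specific variances. It reaches 8 points only for a pooled t-test against a common-variance contrast with an inert low dose.

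These sizes rest on the assumed low-dose effects, on a high-dose effect of 1.5 nmol/l, and on normal data with equal SDs. They are on the absolute-change scale, which SAP 4.2.1 and 10 now make secondary. The SAP's primary endpoint is percent change, with no effect size or SD stated, so the mechanism applies there but the number of points cannot be given.

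**What to change.** In Protocol 11.1 and SAP 7.10.2, specify the gate as the contrast (high + low)/2 minus placebo, estimated from the three randomised arms with arm-specific variances and Satterthwaite degrees of freedom. Keep the three pairwise steps as two-group t-tests (or contrasts with arm-specific variances), in the stated order and at the same 5%. State which form of t-test is meant.

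The cost is a few lines of SAP text and one model statement. Hypotheses, alpha, sample size and data collection do not change. If a pooled t-test was intended and the doses are in fact equal, about 0.5 point of gate power is given up (94.7 to 94.2%). A side benefit is that the two doses keep equal weight in the combined effect if dropout differs between them.
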